15.3. Indemnity

All subjects are fully covered by Coloplast A/S insurance throughout the investigation: [REDACTED]

15.4. Financial conditions

The investigation is initiated and sponsored by Coloplast A/S and Coloplast A/S will compensate the investigator for the time and resources spent on this investigation. The expenses include salary to the investigator and study staff, cost of products, transportations and gift certificates.

The investigation expenses are expected to be approximately [REDACTED] per subject.

Subjects will be compensated for their participation in the study and receives a gift voucher equivalent in value to [REDACTED] per visit 1, 2, 3 and 4, in total [REDACTED] if the subject completes the investigation. The subjects will also be compensated for any transport expenses. Reimbursement of transport expenses are not taxable whereas payment for participation in the study is taxable per local legislations. Subjects will be paid for their participation after each visit and transport expenses will be paid in appropriate portions that justify the administration, throughout investigation period.

All financial agreements with the investigator will be specified in a sponsor investigator Agreement. The Investigator has no financial conflict of interest in the investigation.

16. Informed consent process

[figure not shown]
Written informed consent is obtained from all subjects participating in the investigation after thorough written and verbal information. The information is given by the investigator or his/her representative in the subjects' native non-technical language. Each subject will be fully informed about the aim of the investigation, procedures, potential risks or inconveniences and/or expected benefits and have a minimum of 24h before deciding on participation. The subjects will be informed that their participation is voluntary and that they may leave the investigation at any time, without this having any influence on their further treatment. Furthermore, the subjects will be informed that the investigator, sponsor, sponsor representatives and regulatory authorities can get access to relevant information from patient journals necessary to conduct the investigation and to audit the investigation.

The informed consent signature form includes personally dated signatures of the subject and the investigator or his/her representative responsible for conducting the informed consent process. A copy will be provided to the subject.

If new information is to be given during the investigation, sponsor will inform the investigator, and the new information is given to the subjects by the investigator. If new information becomes available that can significantly affect a subject's future health and medical care that information will be provided to the subject in written form. The Clinical Manager is responsible for writing the information and providing it to investigator that will further provide it to the subjects. If applicable, all affected subjects shall be asked to confirm their continuing informed consent in writing.

This procedure also applies to informed consent obtained from a subject's legal representative. The procedure cannot waive the subjects' legal rights.

17. Adverse events, adverse device effects and device deficiencies

17.1. Adverse events

An adverse event is any untoward medical occurrence, unintended disease or injury, or untoward clinical signs (including abnormal laboratory findings) in subjects, users or other parties, whether or not related to the medical device(s), or the procedures involved. This could include events such as headache or dizziness.

17.2. Adverse device effect

An adverse event, which is related to the use of the investigational medical device, is an adverse device effect, and should be marked as related or possibly related on the adverse event form.

The definition of an adverse device effect includes any event resulting from insufficiencies or inadequacies in the instruction for use, or any malfunction of the medical device, as well as any event resulting from use error or from intentional misuse of the device.

The anticipated adverse device effects are well known in connection with the use of new adhesives. Allergic peristomal skin irritation occurs very rare, but information about possible allergic reactions will be collected.

Temporary redness upon removal of the ostomy tape plate is not considered to be an adverse device effect. However, an abnormal development in the intensity or duration of redness should be considered an adverse device effect.

Table 5 lists anticipated adverse device effects that may occur.

Table 4 Anticipated adverse device effects and their likely incidence rates

ANTICIPATED ADE	INCIDENCE RATE
Peristomal skin irritation (incl. mechanical trauma and skin maceration)	< 10%

Allergic peristomal skin irritation (dermatitis)	< 1%
--	------

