4.1. Description of investigational device

The test products are non-CE marked stoma tape products. The products are adhesive strips designed to support the edges of the ostomy baseplate by providing additional adhesion to the intact peristomal skin. [REDACTED]

[REDACTED]

[REDACTED]

[REDACTED]

[REDACTED]

[REDACTED]

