6.1.1. Inclusion and exclusion criteria

Below, in Table 1 and Table 2 inclusion and exclusion criteria are presented.

Table 1: Inclusion criteria

Inclusion criteria		Justification for inclusion criteria
To be included in the investigation a subject must comply with the following inclusion criteria:		
1.	Has given written informed consent	To ensure that the subject has been given written and oral information regarding the investigation, and know enough about the investigation to decide participation
2.	Be at least 18 years of age and have full legal capacity	To meet the Helsinki declaration
3.	Have had a stoma for more than 1/2 year	To ensure subjects are recovered from ostomy surgery
4.	Have intact skin on the area used in the study (Assessed by investigator, see Appendix 1).	The skin has to be intact in order to explore the peristomal skin after use of ostomy tape
5.	Willing to change baseplate every second day or less frequent	To ensure at least two days wear time and baseplates cannot be changed without changing the tapes

Inclusion criteria		Justification for inclusion criteria
To be included in the investigation a subject must comply with the following inclusion criteria:		
6.	Willing to avoid using Concave baseplate during the study.	The ostomy tape is not designed for this type of baseplate
7.	Willing to avoid the use of barrier creams or similar that affect the skin/adhesive interface under the tape.	Barrier creams may interfere with the study endpoints by interfering with the performance of the ostomy tapes.

Table 2: Exclusion criteria

Exclusion criteria		Justification for exclusion criteria:
A subject is not allowed to participate in case he/she:		
1.	Currently receiving or have within the past 2 months received radio-and/or chemotherapy	The skin undergoes major changes because of radio-and/or chemotherapy, and therefore, the skin might be more fragile to product changes.
2.	Currently receiving or have within the past month received topical steroid treatment in the peristomal skin area or systemic steroid (tablet(injection) treatment	Steroid product on peristomal skin may interfere with the study endpoints by making the peristomal skin thinner and more fragile.
3.	Is pregnant or breastfeeding	Even though the ingredients and the recipes have been approved for humans, their effect on embryos, foetuses, and infants are unknown.

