4.	Having dermatological problems in the peristomal area (assessed by investigator)	The skin has to be intact in order to see a potential damage of the skin.

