2. Mucous membrane

- 3. Intact mucous membrane
- 4. Injured mucous membrane

These definitions shall be considered in product development, product classification, product intended use in instructions for use (IFU) and in promotional material.

Regulatory background

The terms “injured skin”, “injured mucous membrane”, and “intact skin” appear currently in the Medical Device Regulation of 5th April 2017 as follows [1]:

- A. in Annex VIII “Classification Rules”, Chapter I, 2.8:

“Injured skin or mucous membrane” means an area of skin or a mucous membrane presenting a pathological change or change following disease or a wound.

- B. Annex VIII, Chapter III, 4.4 (rule 4):

All non-invasive devices which come into contact with injured skin or mucous membrane are classified as:

- *class I if they are intended to be used as a mechanical barrier, for compression or for absorption of exudates*
- *class IIb if they are intended to be used principally for injuries to skin which have breached the dermis or mucous membrane and can only heal by secondary intent*
- *class IIa if they are principally intended to manage the micro-environment of injured skin or mucous membrane; and*
- *class IIa in all other cases*

- C. in Annex VIII “Classification Rules”, Chapter III, 7.5 (rule 18) [14]:

All devices manufactured utilizing tissues or cells of human or animal origin, or their derivatives, which are non-viable or rendered non-viable, are classified as class III, unless such devices are manufactured utilizing tissue or cells of animal origin, or their derivatives, which are non-viable or rendered non-viable and are devices intended to come into contact with intact skin only”

Coloplast Definitions:

1. Skin

1.a. Intact skin

Intact skin is skin where the basement membrane is unbroken (anatomically based definition). The basement membrane consists of the stratum basale (basal epithelial layer), the basal lamina and the reticular lamina. [2]

The epithelial cells can replicate from the stratum basale and normal anatomical structure and function can quickly be restored [3].

If the basement membrane is broken the vascularized dermis is exposed and the skin is no longer considered intact.

For products intended for pediatric use, please refer additionally to relevant document(s).

1.b. Injured skin

Injured skin is skin presenting pathological changes or changes following disease or trauma.

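### Allergic dermatitis is an anticipated effect of the tapes, but eligibility looks only at the present state of the skin and nobody asks about past allergy

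*Combined protocol and SAP*

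**What the plan says.** Section 4.1 states: "The test products are non-CE marked stoma tape products". Section 17.2 says of the expected harms: "The anticipated adverse device effects are well known in connection with the use of new adhesives". The table there has two rows, one of them "Allergic peristomal skin irritation (dermatitis") at under 1%. The text adds: "Allergic peristomal skin irritation occurs very rare, but information about possible allergic reactions will be collected".

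Table 2 in section 6.1.1 has four exclusions: recent or current radio- or chemotherapy, recent or current steroid treatment, pregnancy or breastfeeding, and "Having dermatological problems in the peristomal area (assessed by investigator"). The reason given for the fourth is: "The skin has to be intact in order to see a potential damage of the skin". In Table 1, inclusion 4 reads: "Have intact skin on the area used in the study (Assessed by investigator, see Appendix 1"). Appendix 1 supplies the definition: "Intact skin is skin where the basement membrane is unbroken (anatomically based definition").

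Section 5.6 gives every arm the comparator and both test products. Section 7.2 has adhesive remover used at tape removal, both at the visits and at home.

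**The concern.** The plan foresees an allergic reaction as a device effect and intends to record it if it occurs, but has no step that identifies people already known to be prone to one. Prior sensitisation can be present while the skin looks normal, so inspecting the skin at V0 would not reveal it.

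Two things are at stake. The first is avoidable exposure of a volunteer to two new adhesives and a comparator. The second is interpretation. Erythema, itch, pain, skin complications and adverse events are all secondary endpoints and are summarised by product. A reaction that reflects a known susceptibility of the person would appear there as if it described the tape.

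**Working it through.** The plan has no figure to reproduce on this point. The main check is to apply the written entry steps to a hypothetical candidate with a known allergy to an adhesive ingredient, clear peristomal skin, and no other bar to entry.

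| Step | What it asks | Result for this candidate |
|---|---|---|
| Recruitment search, 6.2 | Stoma type, age, not using a (redacted) product | Passes on the visible text |
| Phone contact, 6.2 | Goes through the inclusion and exclusion criteria | Passes; no allergy question |
| Inclusion 4, Table 1 | Intact skin, defined anatomically in Appendix 1 | Passes |
| Exclusion 2, Table 2 | Topical peristomal or systemic steroid now or in the past month | Passes unless a recent reaction was treated that way |
| Exclusion 4, Table 2 | Dermatological problems, worded in the present tense and justified by intact skin | Passes |
| V0 procedures, 7.2 | Visual evaluation of the skin | Passes |
| Baseline data, 5.5 | Tape use yes/no, other accessories, usual product | Allergy history not recorded |

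The candidate meets every visible written criterion and, under 5.6, is allocated all three tapes. Section 8 mitigates risk through training in application, removal and storage, which does not address allergy. Section 6.3 requires withdrawal when safety is compromised, but that takes effect after exposure.

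**Background rate, for context only.** Assume that the table's figure of under 1% is a per-subject rate p. The chance of at least one allergic reaction among 12 subjects is 1 − (1 − p)^12:

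- p = 1%: 1 − 0.99^12 = 11.4%
- p = 0.5%: 1 − 0.995^12 = 5.8%
- p = 0.1%: 1 − 0.999^12 = 1.2%

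This describes subjects in general. The documents give no rate for people with a known allergy, so their risk cannot be computed.

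**Effect on product contrasts.** Suppose one subject's erythema is raised by d, and data are complete for 12 subjects.

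- If d applies to all three products, it cancels within the subject: (A + d) − (C + d) = A − C.
- If d applies to one product only, the mean difference involving that product moves by d/12. A reaction to one recipe is also partly information about that recipe.

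The size of d is not given.

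**The case against.** The strongest case against is that several safeguards already exist and that little follows statistically.

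- Exclusion 4 is assessed by the investigator, who could decline such a person.
- Candidates have had a stoma for more than half a year, so a severe adhesive allergy may be uncommon among them.
- Exclusion 2 would remove someone whose recent reaction was treated with steroids.
- Section 8 cites biological safety evaluations.
- Skin photos and questions on pain and itch are completed at each product change.
- The instructions for use are not among the documents and the device description is partly redacted, so a warning may exist there.

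All of this stands as mitigation. None of it requires or prompts the question before first exposure, the test recipes are new, and a warning in the instructions for use would not be an eligibility criterion of this plan.

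A reader might also infer more than the documents support:

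- *That 17.2 contradicts Table 2.* It does not. No rule in the plan says that each anticipated effect needs a matching exclusion.
- *That Table 2 excludes nothing but current skin problems.* It has four exclusions. The gap concerns skin and allergy only.
- *That one sensitised subject would be 1 of 12 (8.3%) against an anticipated rate of under 1%.* Any single event in 12 subjects gives 8.3%, whether or not the person was sensitised beforehand. Likewise, 3 of the 36 subject-by-product results come from every subject. Neither figure measures the gap, and the comparison should not be used.
- *That product comparisons would be materially biased.* A reaction to all three tapes falls largely into the random subject effect that section 10.1 specifies for adherent area and allows for erythema through a similar model. No effect on the primary endpoint has been shown.

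**Conclusion.** The point holds as a modest, inexpensive safety improvement. As written, the criteria admit a person with a known adhesive allergy and clear skin to all three tapes, and no screening step asks for the history. Investigator discretion and later withdrawal do not reliably prevent the first exposure.

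No statistical figure in the plan changes, and the effect on modelled product contrasts is likely small. The by-product descriptive summaries of skin endpoints and the adverse device effect counts are more exposed, because no subject effect is removed from them.

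The conclusion rests on the visible text of the plan. It assumes nothing about how often known allergy occurs in the recruitment database, which the documents do not report, or about what the instructions for use contain.

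**What to change.** Bring Table 2, and the matching synopsis list, into line with section 17.2 by adding an exclusion for known allergy or hypersensitivity to an ingredient of any of the study tapes. Extending it to the adhesive remover is sensible because remover is used at each change, although section 17.2 does not itself mention remover allergy.

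Ask about it during the phone contact in section 6.2 and again at V0, and add the answer to the baseline data in section 5.5 and the flow-chart in 7.3.

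The cost is one line in the criteria, one question asked twice, one data field, and possibly a few fewer eligible candidates. The gain is that foreseeable exposure is avoided and reactions due to known susceptibility stay out of the by-product skin and adverse device effect summaries. The sample size and the analysis model need no change.

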17.3. Device deficiency

A device deficiency is the inadequacy of the investigational medical device or comparator with respect to its identity, quality, durability, reliability, safety or performance. This includes malfunctions, use errors and inadequacy in the information supplied by the manufacturer including labelling.

17.4. Serious adverse events (SAE)

A serious adverse event is an adverse event that:

- Led to death,
- Led to a serious deterioration in the health of the subject, users or other persons as defined by one or more of the following:
 - 1) a life-threatening illness or injury, or
 - 2) a permanent impairment of a body structure or a body function including chronic diseases, or
 - 3) in-patient or prolonged hospitalization, or
 - 4) medical or surgical intervention to prevent life-threatening illness or injury or permanent impairment to a body structure or a body function.
- Led to fatal distress, fatal death or a congenital abnormality or birth defect.

This includes device deficiencies that might have led to a serious adverse event if:

- Suitable action had not been taken, or
- Intervention had not been made, or
- Circumstances had been less fortunate.

These are handled under the serious adverse event reporting.

Planned hospitalization for a pre-existing condition, or a procedure required by the CIP, without serious deterioration in health, is not considered a serious adverse event.

17.4.1. Serious adverse device effect (SADE)

A serious adverse device effect is an adverse device effect that has resulted in any of the consequences characteristic of a serious adverse event.

17.4.2. Anticipated serious adverse device effect (ASADE)

Anticipated serious adverse device effect is any event that by its nature, incidence, severity or outcome has been previously identified in the risk analysis report.

17.4.3. Unanticipated serious adverse device effect (USADE)

An unanticipated serious adverse device effect is a serious adverse device effect which by its nature, incidence, severity or outcome has not been identified in the current version of the risk analysis report.

17.5. Medical care of subjects

Principal investigator shall ensure that adequate medical care is provided to a subject experiencing an adverse event during and after participation in the clinical investigation. All serious adverse events will be followed until a resolution is addressed.

The current status of all ongoing adverse events is documented during site close-out.

17.6. Reporting and timelines

17.6.1. Investigator's reporting responsibilities

- PI must assess all (S)AE's that occur at his/her site.

- All serious adverse events and serious adverse device effects must be reported to sponsor within 24 hours of the site becoming aware of the event.
- A device deficiency that could have led to a serious adverse event but did not because suitable action was taken, intervention had been made or because of fortunate circumstances should be reported to sponsor within 24 hours of the site becoming aware of the event.
- New findings and/or updates in relation to already reported serious events should also be reported to sponsor within 24 hours of the site becoming aware of the event.
- Device deficiencies and all adverse device effects must be reported to sponsor within 10 days of becoming aware of the event.

When reporting the SAE, the relationship to the test material shall be described whether the event is considered

- **Not related**, the event has no temporal relationship with the use of the test material or the procedures.
- **Unlikely related**, the relationship with the use of the test material seems not relevant and/or the event can be reasonably explained by another cause, but additional information may be obtained.
- **Possibly related**, the relationship with the use of the test material is weak but cannot be ruled out completely. Alternative causes are also possible (e.g. an underlying or concurrent illness/ clinical condition or/and an effect of another device, drug or treatment). Cases were relatedness cannot be assessed or no information has been obtained should also be classified as possible.
- **Probably related**, the relationship with the use of the test material seems relevant and/or the event cannot reasonably be explained by another cause, but additional information may be obtained.
- **Definitely related/Causal relationship**, the event has a temporal relationship with the test material use/application or procedures.

All above events must be reported by use of the relevant adverse event/serious adverse event/device deficiency form.

Please report to:

[contact]

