5.1. General

This investigation is a randomised, open-label, comparative, cross-over study, with three test periods.

In total, 12 subjects will be included and randomised, and each subject will have an inclusion visit and four test visits overseen by the Principal Investigator, or delegate. Each subject will be enrolled for three times 7-9 days in total for the entire investigation, thus for a maximum of 27 days – equal to at least 3 baseplates + tape change in each period. The subjects will test two new recipes of ostomy tapes and a comparator product in randomised order.

Between the test visits, the subjects will change products at home. At each product change, subjects will take a photo of the peristomal skin using a smartphone with a specially designed Clinical Trial app installed. Furthermore, they will answer questions about feeling of security, adhesion of tape, comfort and potential skin issues.

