7.2. Visits

Baseline visit (V0):

- Introduction to the study
- Informed Consent and letter of authority signed
- Check of in- and exclusion criteria
- Visual evaluation of skin for inclusion
- Pregnancy test - dipstick (for women of child-bearing potential only)
- Inclusion in study and allocation of subject number
- Collect baseline information
- Possibility to accept interview by User Insight/development engineers/project members

Test visit 1:

- Randomisation
- Instruct subject in use of smartphone and Clinical Trial app and remind the subject to bring it for every study visit
- Remove tape/product with use of adhesive remover
- Photo of peristomal skin (digital camera)
- Acclimatization of peristomal skin for ½ hour
- Photo of peristomal skin after acclimatization (digital camera)
- Measurements of erythema
- Provide randomized test products or comparator products for the subject for change at home and apply 2 ostomy tapes on the peristomal skin (after ostomy product has been applied).
- Provide storage material for used ostomy tapes and adhesive remover
- Instruct and remind the subject to follow the study specific procedures between visits
- Schedule next visit in 7-9 days

Test visit 2 and 3:

- Follow up on subjects use of smartphone and Clinical Trial app and remind the subject to bring it for every study visit
- Ostomy tapes are removed with use of adhesive remover (before removing, mark the lifted tape area with a pen on the adhesive part)
- Photo of peristomal skin (digital camera)
- Photo of skin (smartphone – Clinical Trial App)
- Smartphone: Questionnaire about feeling of security, adhesion of tape, comfort & skin issues in the area covered by the tape
- Acclimatization of peristomal skin for ½ hour
- Photo of peristomal skin after acclimatization (digital camera)
- Measurements of erythema

- Provide randomized test products or comparator products for the subject for change at home and apply 2 ostomy tapes on the peristomal skin (after ostomy product has been applied).
- Provide storage material for used ostomy tapes and adhesive remover
- Instruct and remind the subject to follow the study specific procedures between visits
- Schedule next visit in 7-9 days
- Collect all used tapes and measure the adherent area
- Review AEs/ADEs/SAEs/SADEs
- Possibility to accept interview by User Insight/development engineers/project members

Termination visit 4:

- Follow up on subjects use of smartphone and Clinical Trial app

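### In section 17.6.1 the top and bottom SAE relatedness grades rest on timing alone, so they overlap the middle grades and do not match section 17.2

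*Combined protocol and SAP*

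**What the plan says.** The scale in section 17.6.1 opens with "When reporting the SAE, the relationship to the test material shall be described whether the event is considered" and lists five grades. The two end grades are defined by timing:

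- Not related: "the event has no temporal relationship with the use of the test material or the procedures".
- Definitely related/Causal relationship: "the event has a temporal relationship with the test material use/application or procedures".

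The three grades between them use causal reasoning. Unlikely related applies, among other routes, when "the event can be reasonably explained by another cause". Possibly related covers a weak link that cannot be excluded, and is also the default when relatedness cannot be assessed. Probably related applies when "the relationship with the use of the test material seems relevant and/or the event cannot reasonably be explained by another cause". No section defines a temporal relationship or adds a causal criterion to either end grade.

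Section 17.2 defines an adverse device effect as an adverse event related to use of the investigational device, and says it "should be marked as related or possibly related on the adverse event form". Section 17.4.1 defines a SADE as an adverse device effect with serious consequences. Section 17.4.3 defines a USADE as a SADE not identified in the risk analysis report.

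On exposure, section 5.1 states: "Each subject will be enrolled for three times 7-9 days in total for the entire investigation, thus for a maximum of 27 days".

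**The concern.** A causality scale should separate events caused by the product from events that merely happen during its use. Timing can do this only if subjects spend a meaningful part of follow-up unexposed. Here they hardly do, so the two end grades turn on a feature that nearly every on-study event shares.

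An investigator who follows the text could label as definitely caused by the tape an SAE that has an obvious other explanation. An investigator who ignores the text grades by an unwritten rule, in a study that section 5.7 leaves open-label for everyone but the statistician. Either way, the recorded causality grade, and any SADE or USADE classification or relatedness summary drawn from it, would be hard to interpret.

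**Working it through.** The plan gives no figure to reproduce. The check sets the definitions beside the visit schedule.

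**Step 1. Exposure.** Section 5.1 gives three periods of 7 to 9 days: 3 × 7 = 21 to 3 × 9 = 27 days. Section 7.2 has tapes applied at test visits 1, 2 and 3, with the used ones removed at the same visit from visit 2 on. Table 1 in section 6.1.1 says the baseplate cannot be changed without changing the tapes. No washout is described. The only planned gaps are product changes and the half-hour skin acclimatisation at test visits. Near-continuous wear from visit 1 to visit 4 is inferred from this schedule; the protocol does not state it.

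**Step 2. A test case.** Take an SAE that starts while a test tape is worn and has a clear other cause. Read each grade literally:

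| Grade | Deciding criterion | Met? |
|---|---|---|
| Not related | No temporal relationship | No |
| Unlikely related | Link not relevant, and/or another cause explains the event | Yes |
| Possibly related | Weak link that cannot be fully excluded | Depends on the case |
| Probably related | Link relevant, and/or no other reasonable cause | No |
| Definitely related | Temporal relationship | Yes |

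The event meets the second and fifth grades and fails the fourth. A scale on which an event can be definite without being probable is not ordered. A scale on which one event is both unlikely and definite is not mutually exclusive.

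**Step 3. Where the result stops.**

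- An event after consent at V0 but before the first study tape at visit 1 can still be unrelated to tape use.
- For comparator wear the result is unclear. Section 4.6 says the comparator is not an investigational device, and test material is not defined. Both end grades also count procedures, but removal, photography and erythema measurement are discrete acts rather than continuous exposure.
- The scale is introduced for SAEs. Section 17.6.1 also requires the investigator to assess all events, serious or not, but does not say that non-serious events use these five grades.

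**Step 4. What the grade feeds.** SAEs go to the sponsor within 24 hours (17.6.1) and to authorities within 7 calendar days (17.6.2), whatever their relatedness. A SADE must first be an adverse device effect, so SADE and USADE status depends on the relatedness judgement.

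**Step 5. Match with section 17.2.** That section names two markings, related and possibly related. The five-grade scale has possibly, probably and definitely, but no plain related. Neither section says which of the five grades make an event an ADE or SADE.

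**The case against.** The best defence is that no competent assessor would read the scale this way. The top grade carries the label Causal relationship, three of the five grades weigh relevance or other causes, and an event with an obvious other cause has a natural home in Unlikely related. Temporal relationship may have been meant as plausible timing. Section 17.2 also defines a device effect causally, so ADE status does not come from the timing sentence. The event forms are not in the documents, and related or possibly related may be shorthand for possible and above. The study is exploratory, with no pass/fail criterion and no interim analysis, and suspension under section 18 turns on suspected unacceptable risk, not on a grade.

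Most of this limits the consequence and stands. It does not repair the text. Even if temporal means plausible timing, the top grade still does not require other causes to be excluded, and the bottom grade still has no route for an event that has plausible timing but a clear other cause. The causal definition in section 17.2 adds a conflict with the SAE scale, because neither section says which governs. Without the forms, the mapping between the two sections cannot be confirmed either way; the protocol itself does not give it.

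A reader might infer something stronger: that every adverse event in the test periods would be graded definitely related and none unrelated, and that the ADE and SADE counts by product are therefore unreliable. The documents do not support that. The scale is stated for SAEs, ADEs are defined causally, the status of comparator wear is unclear, and events before visit 1 fall outside the argument. Nothing gives an expected SAE count or shows that any event would in fact be misgraded.

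**Conclusion.** The defect is real and minor. Read literally, the end grades let an SAE that starts during wear of a test tape qualify as definitely related and bar it from being not related, even where another cause explains it. The scale is neither ordered nor mutually exclusive, and it is not reconciled with section 17.2.

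The causality grade and the SADE/USADE classification can be wrong, as can any summary by relatedness. Expedited SAE reporting is unaffected. No rate of misclassification can be derived from the documents, so none is offered.

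The conclusion rests on two assumptions: that tape wear is near-continuous, as the schedule implies, and that temporal relationship carries its ordinary meaning, since the protocol gives no other.

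**What to change.** Revise section 17.6.1, and section 17.2 with it:

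1. Define Definitely related as plausible timing, consistency with a known or plausible effect of the tape or procedure, and reasonable exclusion of other causes, all three together.
2. Define Not related as either no temporal relationship, or a clear explanation by another cause with no plausible link to the tape or procedure.
3. Adjust the middle grades so that each event fits exactly one of the five.
4. State whether test material includes the comparator.
5. State in section 17.2 which of the five grades count as an ADE or SADE, and use the same grades there and on the event forms.

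The cost is wording in two sections and matching response options on the forms. No additional data are collected.
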